2.1.2 Rationale for AZD0466 in treatment of haematological malignancies

AZD0466 is a drug-dendrimer conjugate that consists of the active moiety, the dual Bcl-2/Bcl-xL-specific inhibitor AZD4320, covalently conjugated to a pegylated poly-L-lysine type dendrimer, which gradually releases the active moiety by hydrolysis. AZD0466 was developed to mitigate the nonclinical toxicity findings observed with AZD4320.

Administration of AZD0466 results in lower peak plasma levels of AZD4320 than can be readily achieved by direct infusion of AZD4320 at similar exposure concentrations. Thus, AZD0466 exhibits potent Bcl-2/Bcl-xL-selective inhibition and has PK properties that minimise the potential for C_{max} -dependent Bcl-xL-mediated AEs.

In vitro, AZD0466 induces apoptotic cell death in a variety of tumour cell lines, with particularly broad activity in cell lines derived from haematological malignancies. It also demonstrates significant dose-dependent in vivo anti-tumour activity as a single agent across a range of human tumour xenograft and patient-derived models, including acute lymphoblastic leukaemia (ALL), acute myeloid leukaemia (AML), DLBCL, and small cell lung carcinoma. Enhanced nonclinical activity has also been observed for AZD0466 in combination with many standard-of-care anticancer therapies.

In nonclinical studies, anticipated on-target effects include rapid onset, transient abnormalities of hepatic transaminases, and thrombocytopenia. Based on nonclinical data, reduced QRS amplitude may also be observed at clinically predicted dose ranges. A detailed description of the chemistry, pharmacology, and nonclinical efficacy and safety of AZD0466 is provided in the Investigator's Brochure (IB).

AZD0466 has been administered to 9 patients with advanced solid malignancies at doses declared tolerable in the first-time-in-human study (D8240C00003). No dose-limiting toxicities (DLTs) have been recorded (data on file, AstraZeneca).

A detailed description of the chemistry, pharmacology, and nonclinical efficacy and safety of AZD0466 is provided in the IB.

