2.2 Benefit-Risk Assessment

AZD0466 has dose-dependent in vivo anti-tumour activity as a single agent across a range of human tumour xenograft and patient-derived models, including haematological malignancies. Enhanced nonclinical activity has also been observed for AZD0466 in combination with many standard-of-care anticancer therapies.

Potential risks of AZD0466 may be anticipated due to its mechanism of action as a dual Bcl-2/Bcl-xL-specific inhibitor, published literature on clinical use of Bcl-2 and Bcl-2/Bcl-xL inhibitors, and observations from nonclinical studies of AZD0466 (drug-dendrimer conjugate)

and AZD4320 (active moiety). Important potential risks of AZD0466 include thrombocytopenia, hepatotoxicity, and QRS amplitude decrease. Potential risks of AZD0466 include tumour lysis syndrome (TLS), hypocellularity of the bone marrow and lymphoid tissue (neutropenia, lymphopenia, anaemia), thymus and spleen effects, pancreatic toxicity, DDIs, reproductive toxicity, and infusion site reactions. No safety findings emerged from the first-time-in-human study (D8240C00003) that would preclude investigation of AZD0466 in patients with advanced haematological malignancies.

The dosing schedule for AZD0466 utilises an intra-patient dose ramp-up schedule to mitigate the risk of TLS ([Roberts et al 2016](#)). The study protocol incorporates mandatory safety monitoring procedures, dose modification guidelines (Section [6.6](#)), and additional guidance for management of specific AEs ([Appendix F](#)). The study will be performed in accordance with ethical principles that have their origin in the Declaration of Helsinki and are consistent with International Council for Harmonisation (ICH) Good Clinical Practice (GCP), and applicable regulatory requirements.

The available nonclinical and clinical information supports an acceptable benefit-risk assessment for investigation of AZD0466 in patients with advanced haematological malignancies for which there are limited treatment options.

Additional considerations for the benefit-risk assessment of AZD0466 specific to individual modules are described in the respective modules.

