6.6.5 Cardiac findings

AZD0466 should be withheld if any of the following occur at any time during study treatment:

- Symptomatic tachycardia
- Symptomatic hypotension
- QTcF shortening by 60 milliseconds compared to baseline, or interval value < 340 milliseconds, confirmed on at least 2 separate ECGs recorded 5 minutes apart
- QTcF prolongation of > 500 milliseconds or QTcF prolongation from baseline by 60 milliseconds, confirmed on at least 2 separate ECGs recorded 5 minutes apart
- Any other cardiac findings of CTCAE Grade ≥ 2 if considered by the Investigator to be clinically significant

AZD0466 should be permanently discontinued if a CTCAE \geq Grade 3 cardiac AE of any duration occurs during study treatment, if considered by the Investigator to be related to study treatment.

Patients should be monitored closely including continuous ECG monitoring as clinically indicated (including for QTcF prolongations > 500 milliseconds) and until such a time as deemed safe to discontinue monitoring by medical review, with cardiologist input considered in the instance of abnormal ECG findings. AZD0466 may be restarted after resolution of

cardiac findings to the patient's baseline at the discretion of the Investigator and after discussion with the Medical Monitor.

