8.3.12 Adverse Events of Special Interest

An adverse event of special interest (AESI) is an AE, serious or non-serious, that is of scientific and medical interest specific to the understanding of the study treatment and may require closer monitoring, with collecting of additional information by the Investigator and reporting these to the sponsor. The rapid reporting of AESIs by the Investigator allows ongoing surveillance of these events in order to further characterise and understand them in relation to the use of the study treatment. All AESIs should be recorded in the eCRF as soon as possible, preferably within 24 hours. All AESIs that are also serious (ie, are SAEs) should be reported to AstraZeneca Patient Safety within 24 hours, as per safety reporting requirements.

In this study, the following are considered to be AESIs:

- Tumour lysis syndrome ([Appendix G](#))
- Hepatotoxicity, including potential Hy's Law, drug-induced liver injury (DILI), and bilirubin increase with transaminase (ALT or AST or both ALT and AST) increase
- QRS amplitude decrease

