11.6.2.6 Electrocardiograms

Digital 12-lead ECGs (triplicate ECGs, all 3 within a 5-minute time period) will be obtained after the patient has been resting in a supine position for at least 10 minutes. ECGs will be measured before vital signs and prior to PK blood draws at all matched PK sample timepoints. A standardised ECG machine provided by the central ECG vendor should be used and the patient should be examined using the same machine throughout the study, where feasible.

If an unscheduled ECG is done at any time, then an electrolyte panel (Section 11.6.2.9) must be collected to coincide with ECG testing.

Central ECG reads will be utilised during this study. Standard ECG parameters to be determined will include HR/RR, PR, QRS, QT, and QTcF (QT interval corrected for HR using Fridericia's formula) intervals.

After the ECGs have been recorded, the Investigator or designated physician will review each of the ECGs at all timepoints for the presence of abnormalities (including rhythm, ECG intervals, or repolarisation abnormalities) and may refer to a local cardiologist if appropriate. A paper copy of the ECG should be filed in the patient's medical records. For all ECGs, an overall evaluation and interpretation should be recorded by the Investigator or designated physician. Any clinically significant abnormalities detected require a confirmatory ECG. In

case that the centrally provided ECG machine is unavailable or technical issues occur that preclude correct measurement, local ECGs (using the site owned device) may be performed instead.

See Section 6.6.5 for management of cardiac findings and cardiovascular parameters that require treatment to be withheld or increased monitoring. Twelve-lead centrally-read digital ECGs will be performed in triplicate and should be assessed as specified in the SoA (Table 16 and Table 17), and in Table 18).

Table 18 Safety ECG Timepoints and Holter ECG extractions (Module 1)

Study period	Day	Timepoint	Part A and Part B	
			Holter ECG extractions (for PK purpose)	TriPLICATE Safety ECGs (for safety purpose)
Screening	-28 to -1	Baseline	-	X
Cycle 1	1	Pre-infusion	-	X ^a
		End of the infusion (+10 min)	-	X ^a
	2	24 hours after the start of the Day 1 infusion (\pm 2 hours)		X
	4	Pre-infusion	-	X ^a
		End of the infusion (+10 min)	-	X ^a
	5	24 hours after the start of the Day 4 infusion (\pm 2 hours)		X
	8	Pre-infusion	X	X ^a
		30 min after start of infusion (\pm 5 min)	X	-
		End of the infusion (+10 min)	X	X ^a

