11.6.2.7 Cardiac MUGA/MRI/ECHO

A cardiac MUGA/MRI/ECHO to assess LVEF will be conducted. The modality of the cardiac function assessments must be consistent within a patient ie, if ECHO is used for the screening assessment then ECHO should also be conducted at subsequent assessments. A 28-day follow-up assessment will be required if an on-treatment assessment was abnormal at the time of discontinuation of study treatment, to confirm reversibility of the abnormality. The patients should also be examined using the same machine and operator whenever possible.

Unscheduled assessments should be performed as clinically indicated, including after a clinically significant ECG finding (T wave inversion/flattening, significant QRS amplitude changes or symptomatic patient, etc). In case of any T wave abnormality, the ECHO, MRI, or MUGA should be repeated at the EoT visit to address the question of recovery during the off-treatment period.

Cardiac MUGA/MRI/ECHO should be performed (as specified in the SoA in [Table 16](#) and [Table 17](#)) as follows:

- Screening
- Cycle 2 Day 8
- Every third cycle from Cycle 5 (ie, Cycle 5, 8, 11, etc) on Day 8
- EoT visit

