12.6.2.6 Electrocardiograms

Digital 12-lead ECGs (triplicate ECGs, all 3 within a 5-minute time period) will be obtained after the patient has been resting in a supine position for at least 10 minutes. ECGs will be measured before vital signs and prior to PK blood draws at all matched PK sample timepoints. A standardised ECG machine provided by the central ECG vendor should be used and the patient should be examined using the same machine throughout the study, where feasible.

If an unscheduled ECG is done at any time, then an electrolyte panel (Section 12.6.2.9) must be collected to coincide with ECG testing.

Central ECG reads will be utilised during this study. Standard ECG parameters to be determined will include HR/RR, PR, QRS, QT and QTcF (QT interval corrected for HR using Fridericia's formula) intervals.

After the ECGs have been recorded, the Investigator or designated physician will review each of the ECGs at all timepoints for the presence of abnormalities (including rhythm, ECG intervals, or repolarisation abnormalities) and may refer to a local cardiologist if appropriate. A paper copy of the ECG should be filed in the patient's medical records. For all ECGs, an overall evaluation and interpretation should be recorded by the Investigator or designated physician. Any clinically significant abnormalities detected require a confirmatory ECG. In case that the centrally provided ECG machine is unavailable or technical issues occur that preclude correct measurement, local ECGs (using the site owned device) may be performed instead.

See Section 6.6.5 for management of cardiac findings and cardiovascular parameters that require treatment to be withheld or increased monitoring. Twelve-lead centrally-read digital ECGs will be performed in triplicate; collection times are from the start of AZD0466 infusion.

ECGs should be performed as specified in the SoA [Table 25](#) and [Table 26](#), and [Table 27](#).

Table 27 PK Timepoints and Corresponding Safety ECG Timepoints (Module 2)

Study period		Day	Timepoint	TriPLICATE Safety ECGs	
Screening		-28 to -1	Baseline	X	
Cycle 1	Period 1	1	Pre-infusion	X ^a	
			End of the infusion (+10 min)	X ^a	
		2	24 hours after the start of the Day 1 infusion (±2hours)	X ^a	
		4	Pre-infusion	X ^a	
			End of the infusion (+10 min)	X ^a	
		5	24 hours after the start of the Day 4 infusion (±2 hours)	X	
		8	Pre-infusion	X ^a	
			End of the infusion (+10 min)	X ^a	

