4.14.8 ECGs

The following parameters will be assessed in 12-lead ECGs:

- PR-interval (msec).
- QRS-duration (msec).
- QT-interval (msec).
- QT-interval corrected using the Fridericia correction formula (QTcF) (msec).
- RR-interval (msec).
- Heart rate (beats per minute [bpm]).

The ECG will be evaluated by the Investigator as 'Normal', 'Abnormal'.

All ECG parameters will be listed by patient including changes from baseline for numeric ECG parameters.

Descriptive statistics for the means of the triplicate ECG measurements in absolute values and changes from baseline will be presented by dose level/cohort as appropriate. The values used for this summary are the average of the three measurements of the triplicate ECG.

A shift table for the overall ECG assessment from baseline to the worst (abnormal) on-treatment assessment will be created.

Subject profiles will be plotted for the means of the triplicate ECG measurements in absolute values.

QTcF outliers (defined as values following study treatment that are greater than 470 msec or increases from baseline greater than 30 msec) will be summarised using cumulative counts and percentages under the following categories:

- Absolute value > 470 msec

- Absolute value > 480 msec
- Absolute value > 500 msec
- Change from baseline > 30 msec
- Change from baseline > 60 msec
- Absolute value > 470 msec and change from baseline > 30 msec
- Absolute value > 500 msec and change from baseline > 60 msec.

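### QRS amplitude decrease is a named important risk and AESI, but neither document plans to measure or define it; separately, the SAP's QTcF outlier table leaves out the protocol's own shortening criteria

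*Protocol*

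**What the plan says.** **The risk.** Protocol 2.1.2 reports from nonclinical work that "reduced QRS amplitude may also be observed at clinically predicted dose ranges". Section 2.2 states: "Important potential risks of AZD0466 include thrombocytopenia, hepatotoxicity, and QRS amplitude decrease". Section 8.3.12 lists "QRS amplitude decrease" as an AESI, and SAP 4.14.4 repeats it; neither adds a definition. In 11.6.2.7 (and 12.6.2.7 for Module 2), "significant QRS amplitude changes or symptomatic patient" is among the ECG findings that call for an unscheduled LVEF assessment, without saying what counts as significant.

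**The measurement.** For Module 1, 11.6.2.6 states: "Standard ECG parameters to be determined will include HR/RR, PR, QRS, QT, and QTcF". For Module 2, 12.6.2.6 states: "Standard ECG parameters to be determined will include HR/RR, PR, QRS, QT and QTcF". Both sentences end by calling these intervals. The Holter section (11.6.2.6.1) names the same intervals plus arrhythmia. SAP 4.14.8 lists QRS only as "QRS-duration (msec", that is, a duration, together with PR, QT, QTcF, RR, heart rate and the investigator's normal/abnormal rating.

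**QTcF.** Among the findings for which Protocol 6.6.5 withholds drug is "QTcF shortening by 60 milliseconds compared to baseline, or interval value < 340 milliseconds", confirmed on repeat ECGs. SAP 4.14.8 defines QTcF outliers only as high values or increases.

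**The concern.** QRS duration and QRS amplitude are different quantities: one is a time, the other a voltage. Measuring the first says nothing direct about the second. The plan names the second as a risk it expects might appear at clinical doses, and then specifies only the first.

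Change from baseline in ECGs is part of the primary safety endpoint (Protocol Section 3, SAP 2.1). A reader of the study report will look to the AESI table to see whether the nonclinical signal carried over to patients, and at which dose levels. If that table counts only what investigators happened to notice and report, a zero or low count is hard to interpret. It could mean no effect, a small effect, or an effect that was not looked for in a standard way.

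The QTcF issue is smaller. The outlier table is where a reader expects to find threshold crossings, and one pair of thresholds that the protocol acts on has no row there.

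**Working it through.** No formula applies, and the plan gives no figure to reproduce. The check sets the texts side by side.

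1. **Is the amplitude a named risk?** Yes, in Protocol 2.1.2, 2.2 and 8.3.12 and in SAP 4.14.4.

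2. **Does any planned measurement return an amplitude?** The central read (11.6.2.6, 12.6.2.6) and the Holter read (11.6.2.6.1) name heart rate, intervals and arrhythmia. SAP 4.14.8 names PR, QRS duration, QT, QTcF, RR and heart rate. Result: 0 of 6 SAP parameters is an amplitude.

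3. **Is there a definition?** Neither document gives a lead, a baseline comparison or a numerical change that makes a decrease an AESI.

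4. **How are the other two AESIs handled?** Tumour lysis syndrome has laboratory and clinical criteria and grades (Protocol Appendix G) and its own SAP output (4.14.11). Hepatotoxicity has numerical Hy's Law criteria (Appendix E), and SAP 4.14.6 tabulates and plots liver tests for patients above stated multiples of the upper limit. QRS amplitude decrease has no counterpart to either: its only output is the count of reported events in SAP 4.14.4.

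5. **What recordings are already scheduled?** Triplicate digital 12-lead ECGs. For Module 1 Cycle 1, Table 18 gives, for Days 1, 2, 4, 5, 8, 9, 10, 11, 15, 16, 22, 23, 29 and 30 in turn: 2+1+2+1+2+1+1+1+2+1+2+1+2+1 = 20 timepoints. These are intended for central reading, although 11.6.2.6 allows a site-owned device when the central machine is unavailable or has technical problems.

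6. **QTcF outlier categories.** The seven in SAP 4.14.8 are: above 470, above 480 and above 500 msec; increase above 30 and above 60 msec; and two combinations of a high value with an increase. Result: 0 of 7 captures a value below 340 msec or a decrease of 60 msec.

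7. **Are QTcF decreases lost?** No. SAP 4.14.8 lists values and changes by patient, summarises values and changes by dose level, and plots subject profiles. Under SAP 4.2 the descriptive statistics include the minimum.

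**The case against.** A reader might infer that the trial cannot show whether a QRS amplitude decrease occurred, or that the AESI count is near zero by construction. The documents support neither reading. Under 11.6.2.6 and 12.6.2.6 the investigator reviews every ECG at every timepoint and records an interpretation, and any clinically significant abnormality needs a confirmatory ECG. The abnormalities named there are examples, so amplitude is not excluded. The LVEF section itself treats an amplitude change as an ECG finding to act on. A reported AESI is listed and counted under SAP 4.14.4. Nothing in the documents gives the sensitivity of this review, so no claim about how many events it would miss can be made.

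Four further points are fair:

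- The lists of central-read parameters are not worded as exhaustive.
- Table and listing specifications sit in a separate document (SAP Section 1) that is not available here, so some output detail may be there.
- LVEF is measured on a schedule and analysed (SAP 4.14.9), so a related functional effect is quantified.
- The study was terminated and Part B was not initiated (SAP Section 1). Feeding amplitude results to sites or the Safety Review Committee during the study can no longer help.

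What survives is the absence of a standardised measurement. Investigator review without a definition gives reports, not a rate or a size that can be compared between dose levels. LVEF does not stand in for a voltage. SAP 4.14.8, which fixes the planned ECG analysis, names only QRS duration.

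**Conclusion.** The point holds in a limited form. QRS amplitude decrease is a named important potential risk and AESI with no planned objective measurement and no definition in either document. Its incidence and size rest on unstandardised investigator review, so a zero or low count is not evidence that the effect is absent. How far such a count would understate the truth cannot be stated from the documents.

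The QTcF gap is one of presentation only. The two shortening criteria in 6.6.5 have no row in the outlier table, but the underlying values and changes are reported elsewhere in the outputs.

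The conclusion about what is missing rests on the text of the two documents alone. Whether the amplitude gap can still be closed depends on two things the documents do not state: that the ECG waveforms were retained, and that the vendor can extract amplitude from them.

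**What to change.** **Amplitude.** In Protocol 11.6.2.6 and 12.6.2.6, add QRS amplitude to the centrally read parameters from the triplicate digital ECGs already scheduled. In SAP 4.14.8, summarise amplitude and its change from the pre-dose baseline by dose level. Since the study has ended, in practice this is a retrospective read of stored recordings, if the two feasibility assumptions hold; timepoints recorded on local devices may have to be left out. If it cannot be done, state in the CSR that the AESI count does not rest on measured amplitude and that a low count should not be read as absence.

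**QTcF.** In SAP 4.14.8, add two outlier categories that mirror the figures in 6.6.5: value below 340 msec, and decrease from baseline of at least 60 msec. These use data already collected. They count threshold crossings, not confirmed holds, because 6.6.5 also requires confirmation on at least two ECGs.

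**Consistency.** Ask the sponsor to reconcile the undefined amplitude trigger in 11.6.2.7 and 12.6.2.7 with the AESI in 8.3.12. A numerical trigger for the LVEF assessment would be a clinical rule and is not proposed here; the analysis change does not need one.

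**Cost.** A small change to the vendor's specification and a few extra output rows. No new visits, procedures or readers are needed, and no dosing or hold rule changes.

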11.6.2.6.1 Continuous 12-lead ECG Recordings (Holter)

Continuous recordings of 12-lead ECGs (12-lead Holter devices) will be performed for the purpose of PK modelling, which allows monitoring of PR, QRS, QT, QTcF, RR intervals, and arrhythmia and to allow extraction of replicate 12-lead ECGs. The timing of ECGs may be altered depending on the emerging PK profile. Recording should be performed (as specified in the SoA in Table 16 and Table 18) on Day 8 of Cycle 1, with recording commencing pre-infusion to cover the 24-hour timepoint (prior to PK sampling). The standardised 12-lead Holter device will be provided by the central ECG vendor who will provide the central ECG reads.

The 12-lead Holter devices will always be fitted and safely removed by the Investigator or a trained designee.

The schedule of continuous ECG recordings may be increased, reduced, or stopped at any time during the study, if supported by emerging data and with the agreement of the SRC.

11.6.2.7 Cardiac MUGA/MRI/ECHO

A cardiac MUGA/MRI/ECHO to assess LVEF will be conducted. The modality of the cardiac function assessments must be consistent within a patient ie, if ECHO is used for the screening assessment then ECHO should also be conducted at subsequent assessments. A 28-day follow-up assessment will be required if an on-treatment assessment was abnormal at the time of discontinuation of study treatment, to confirm reversibility of the abnormality. The patients should also be examined using the same machine and operator whenever possible.

Unscheduled assessments should be performed as clinically indicated, including after a clinically significant ECG finding (T wave inversion/flattening, significant QRS amplitude changes or symptomatic patient, etc). In case of any T wave abnormality, the ECHO, MRI, or MUGA should be repeated at the EoT visit to address the question of recovery during the off-treatment period.

Cardiac MUGA/MRI/ECHO should be performed (as specified in the SoA in [Table 16](#) and [Table 17](#)) as follows:

- Screening
- Cycle 2 Day 8
- Every third cycle from Cycle 5 (ie, Cycle 5, 8, 11, etc) on Day 8
- EoT visit

